
Study Objectives:
 
 
• Primary
 
• Secondary
 
	
The primary objective is to ascertain if the addition of Cana improves CD34+ cell function and gene expression in type 2 diabetes patients, which will be correlated to improvement in 24hr urinary protein estimation and creatinine clearance (obtained via micro-albumin/creatinine ratio from a spot urine sample).
 
The secondary objective is to correlate the cellular outcome measures with other measures of endothelial function such as:
 
 
1. Arterial stiffness measures with Pulse wave analysis and pulse wave velocity measurements.
 
2. Serum biochemistry looking at surrogates of endothelial health, endothelial inflammation, appetite controlling hormone levels and fasting glucose, insulin and lipid profile.
 
3. Resting Metabolic Rate measurement
 
 
Study Outcome Measures:
 
Primary:
 
To investigate the effect of Cana on Endothelial function in patients inadequately controlled (HbA1C <math>\geq</math> 7.0 % to <math>\leq</math>10%) while being treated with a stable dose of certain anti-diabetic drugs.
 
 
• Cellular markers. We will study pre and post Cana treatment changes in number, function and gene expression of patients' peripheral blood-derived CD34+ cells.
 
• Renal Function Estimation: 24hr urinary protein estimation, creatinine clearance and urine exosome study.
 
 
Secondary:
 
To investigate the effect of Cana treatment on:
 
 
• Serum endothelial inflammatory markers including high sensitivity C-reactive protein (hs-CRP), IL-6, TNF-alpha and fasting lipid profile.
 
• Glycemic control will be evaluated by measuring fasting blood glucose, insulin, and HbA1c levels and assessing insulin resistance using HOMA-IR.
 
• Adiposity, measured using a body composition analyzer scale, measured as percentage body fat.
 
• Creatinine clearance estimation.
 
• Vessel health will be assessed by systolic and diastolic blood pressure and Arterial stiffness assessed using Vascular Flow and wave measurement equipment, SphygmoCor CP system from ATCOR.
 
• Central and aortic blood pressure estimated by the sphygmocor system.
 
• Resting Metabolic Rate (RMR, similar to Resting Energy expenditure measurement) at baseline, midway point (week 8) and post therapy.
 

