	
20. Active wounds or recent surgery within 3 months. 21. Untreated hyper/hypothyroidism
 
Additionally, patients who are active smokers, patients who are pregnant, nursing women, and post-menopausal women who are on estrogen hormone replacement therapy (not including oral contraceptives) will be excluded.
 
Detailed Inclusion / exclusion criteria are listed on pages 12-15 of the protocol.

Criteria for Evaluation: (Efficacy, safety, stopping rules, etc.)
	
Subjects will be phone screened to determine initial eligibility. If the phone-screening indicates possible eligibility, then the subjects will come to an in-person screening visit at week -2, then evaluated for end points at weeks 0, 8 and 16. Follow up phone call will be done 30 days after last dose of study drug to assess for adverse effects.
 
Study participation will be stopped for adverse effects at the discretion of the study investigator. Subjects may stop study participation at any time and for any reason.

Statistics:
	
The total sample size is requested, after accounting for attrition over the 16-week period, is 20 subjects per group or 40 subjects total. Sample size estimates were based on the effects of exercise on CD34+/KDR+ cells as described in the literature. The effect of a single session, as well as extended training, on healthy subjects or those with existing cardiovascular conditions appears to increase the CD34+/KDR+ cells.
 
This is a pilot study; as a result appropriate power calculation is not feasible. We however did conduct power analysis, which provided us with 73% power (see statistics section). A p-value of less than 0.05 will be considered statistically significant.

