Our preliminary data indicates that mRNA gene expression of both SGLT1 and SGLT2 are noted on human CD34+ cells however only SGLT2 mRNA gene expression is up-regulated several fold in human CD34+ cells in presence of hyperglycemia (20mM glucose). However non primary commercially obtained human endothelium (HUVEC) do not show similar results. An explanation could be SGLT2 expression decreases as the cell transitions from progenitor to mature endothelium. From these results we believe SGLT2 inhibitor will be effective on progenitors and not mature endothelium. We therefore hypothesize that CD34+ cells will be an ideal biomarker to study the effect of the drug. It is possible that Cana, by blocking SGLT2 receptors, may influence other CD34+ cell surface receptors including other glucose transporters and influence its function (most importantly migration). If a particular medication positively influences stem/progenitor cell migration then that medication can positively influence endothelial dysfunction and vascular complications from diabetes. We are particularly interested to note effect of Canagliflozin, a SGLT2 inhibitor on other glucose transporters such as GLUT 1 and 4 while looking at SGLT 1 and 2 on CD34+ cells. It will be helpful to discern these effects particularly when choice of oral diabetic medication in a type 2 diabetes population is practically limited to metformin, DPP4 inhibitors and SGLT2 inhibitors. We plan to investigate the effect of Cana on CD34+ cells, in a placebo matched study. We plan to recruit subjects with type 2 diabetes with the following characteristics: 1) overweight, mild and moderately obese (BMI=25.0-39.9); 2) individuals with type 2 diabetes with inadequate control, HbA1C= 7 to 10.0%, on any combination of the following anti-diabetic therapies: metformin (1-2 grams), insulin, GLP-1 agonists, a DPP-IV inhibitor, or sulfonylureas 3) with no current macrovascular complications. As per the ADA [2], Metformin, insulin, GLP-1 agonists, DPP-IV inhibitors, and sulfonylureas are all 1st line of care along with life-style modification. While Metformin on its own may affect inflammatory biomarkers, the effect is minimal at best, particularly in presence of endothelial dysfunction. For accurate comparison, both placebo and the Canagliflozin group will be on any combination of the following anti-diabetic therapies: metformin (1-2 grams), insulin, GLP-1 agonists, a DPP-IV inhibitor, or sulfonylureas We will recruit a total of 40 patients (20 individuals/per group) with approximately a 20% drop out rate over two years and we hope to retain 32 individuals (16/group). Individuals in each group will be matched by sex, age, and race. Participants will be assessed at baseline (week 0), and at 2 and 4 months of drug intake.

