# 2 STUDY OBJECTIVES

## PRIMARY OBJECTIVE

**To determine whether 4 months of Canagliflozin modifies CD34+ cell number, gene expression and migration function.**

## PROTOCOL FOR OBTAINING CD34+ CELLS:

We will obtain a total of approximately 95 mL of peripheral blood per visit. Of these 95 mL, 60-70 mL will be used to obtain CD34+ cells from mononuclear cell (MNC) population and 25-35 mL for biochemistry and plasma ELISA assays. MNC will be obtained from whole blood similar to protocols described before. MNCs will be put through CD34 magnetic bead column to obtain CD34+ cells (Miltenyi Biotec). Purity of CD34+ cells, post sort, usually is above 90%, to be verified by FACS analysis.

- A. From Mononuclear (MNC) population (pre CD34+ magnetic column sorting): We will assess the proportion of various cell types, progenitor stems and mature cells in MNCs to note if Cana influences stem vs non stem cell pool such as percentage of : CD34, CD309 (VEGFR2-KDR), CD184 (CXCR4), receptor substrate for SDF1 alpha, CD31 (PECAM-1, a mature circulating endothelial cell marker), CD133 (a progenitor marker), CD144 (Vascular Endothelial cadherin), Sytox Blue OR Propidium Iodide staining (to detect apoptotic cells).
- B. MNC cells (prior to CD34 magnetic bead sorting) will be also used to assay CFU Hill Colony forming unit (Stem Cell Technologies- Cat#05900) media for Colony Forming unit (CFU) Assay. CFU will be counted on 5-7 days post plating (from initial plating).
- C. From CD 34+ cell population (Post Sorting):
  - a. Migration Assay using SDF1Alpha concentrations of 0, 10, 100ng/ml and VEGF-A concentrations of 20 and 50 ng/ml, using 150,000 cells in 300ul serum free cell suspension media per insert.
  - b. Gene expression studies. Genes to be assessed on sorted CD34 positive cells:

- i. Endothelial lineage cell surface markers: CD34, VEGFR2 (KDR), CD31, CD144
- ii. For Anti-oxidant gene expression: Superoxide dismutase (SOD) 1, 2 and 3, catalase, glutathione- peroxidase.
- iii. Apoptosis pathway: p53, p21, Bcl2, caspase-3
- iv. Endothelial Function Assay Gene: endothelial Nitric Oxide Synthase, von-Willebrand's Factor
- v. Genes associated with progenitor cell chemotaxis: VEGF-A, SDF1 alpha, CXCR4.

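### The primary objective spans several unranked CD34+ domains, stated inconsistently, with no named primary endpoint or success rule and no control of the 0.05 level across outcomes

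*Combined protocol and SAP*

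**What the plan says.** **Cellular measures.** The primary objective in Section 2, and again under Research Study Design and Methods in Section 6, is whether four months of canagliflozin changes CD34+ cell number, gene expression and function. Section 2 narrows function to migration. The synopsis outcome list agrees on three domains: "pre and post Cana treatment changes in number, function and gene expression". The synopsis objective sentence, however, names only function and gene expression.

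**Renal measures.** The synopsis primary outcomes also include 24-hour urinary protein, "creatinine clearance and urine exosome study". Its secondary outcomes then list "Creatinine clearance estimation" as well. The Inclusion Criteria text in Section 3 counts renal function among the prime outcomes. Sections 2 and 6 place the same urine measures under the secondary objective. Appendix A calls the exosome endpoint exploratory.

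**Testing.** The synopsis Statistics row says "A p-value of less than 0.05 will be considered statistically significant". It also says "This is a pilot study; as a result appropriate power calculation is not feasible". Data Analysis in Section 7 describes one mixed model for an unnamed outcome and stresses the group-by-time interaction. Time is continuous, and further models treat it as a class variable to look for non-linear change. The text after the model equation refers to two indicator variables for the interaction. An adjustment for multiple comparisons is promised for pairwise comparisons of group slopes once the interaction is significant.

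**The concern.** The plan does not say which result would answer the primary question. One significant gene or one migration condition could be reported as meeting the objective, and a null result for cell number would not count against it. Where several primary results are each judged at 0.05, the chance that at least one is significant by luck exceeds 5%, and nothing in the plan limits it.

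The hints that might settle the matter point in different directions. The sizing text in Section 7 uses CD34+ cell number, but the synopsis says "Sample size estimates were based on the effects of exercise on CD34+/KDR+ cells as described in the literature", which is a different cell population. The Introduction expects the drug to "influence its function (most importantly migration"), and Section 2 also singles out migration.

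**Working it through.** The plan gives no error rate across outcomes, so there is no figure of its own to reproduce.

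**1. How many tests.** The plan does not say, so three readings are shown. Renal measures are left out of all of them.
- One test per domain (number, function, gene expression): 3.
- The protocol's own gene sets: 5 sets + 1 migration + 1 colony-forming assay = 7, from the Section 6 list.
- Every listed laboratory measure. Genes: 4 lineage + 5 antioxidant + 4 apoptosis + 2 endothelial function + 3 chemotaxis = 18. Migration contributes 5 conditions: "Migration Assay using SDF1Alpha concentrations of 0, 10, 100ng/ml and VEGF-A concentrations of 20 and 50 ng/ml". Section 6: 18 + 5 + 1 colony assay = 24. Section 2 adds 7 flow-cytometry items: 24 + 7 = 31.

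The last count is a reading of laboratory lists. It falls to 20 to 27 if migration is one assay. It is 23 to 29 if SDF1-alpha at 0 ng/ml is a control condition and the viability stain is not counted. The Section 6 list contains no assay for cell number, although its objective names it.

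**2. Chance of at least one false positive.** For k independent tests at 0.05 with no true effect, this is 1 − 0.95^k:
- k = 3: 1 − 0.857 = 0.143
- k = 7: 1 − 0.698 = 0.302
- k = 24: 1 − 0.292 = 0.708
- k = 31: 1 − 0.204 = 0.796

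For correlated measures I used two-sided normal tests with a common correlation, solved by numerical integration. The values 0.5 and 0.8 are assumptions.

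| Tests | Independent | Correlation 0.5 | Correlation 0.8 |
|---|---|---|---|
| 3 | 14% | 13% | 10% |
| 7 | 30% | 23% | 15% |
| 24 | 71% | 46% | 24% |
| 31 | 80% | 51% | 26% |

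**3. What the Section 7 adjustment covers.** It starts only after the interaction is significant, and it concerns contrasts inside that outcome's model. With two arms there is only one pair of group slopes. It therefore does nothing about the number of outcomes tested.

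**4. Which term decides.** The time point is implied: four months in the objective, and week 16 as the end-of-treatment visit in the Section 6 schedule. The test is less settled. The interaction could be the linear slope difference (1 parameter) or the class-time version (2 parameters, for weeks 8 and 16). Data Analysis leans towards the former, and the remark about two indicator variables fits the latter.

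**The case against.** The strongest reply is that this is a 40-patient pilot and that the laboratory lists describe assays, not endpoints. On that view nobody intends 24 or 31 primary tests, and the 71% to 80% figure describes a trial that was not planned. Much of this stands. No section says that each measure gets its own primary test. Five of the seven flow markers (CD34, KDR, CXCR4, CD31, CD144) also appear in the gene list, so independence is the least plausible case. The full-list figures are an upper bound. The concern survives because three domain-level tests alone give two to nearly three times the 5% level, and because the same synopsis row that calls the study a pilot also sets a significance rule.

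On time coding, Section 7 can fairly be read as making the continuous-time interaction the main test, with the class-time models as a supplement. That reading is reasonable but not fixed, given the two indicator variables.

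The renal measures may have been meant only to support the cellular results: the synopsis objective says the cellular results will be correlated with them. That would be a sensible role, but it is not what the synopsis outcome list or the Inclusion Criteria text says.

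A reader might infer that the unblinding procedure in Section 4 makes matters worse, because it lets clinical outcomes be unblinded before the cellular data are analysed. That adds little. It applies only in unforeseen circumstances, with the sponsor consulted and the data already acquired and compiled. The open choice comes from the unnamed endpoint.

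**Conclusion.** The point holds and should be fixed. The primary set is unranked, the sections disagree on whether cell number and the renal measures belong to it, and no rule controls error across outcomes. The chance of at least one false-positive primary cellular result is 10% to 14% with one test per domain, 15% to 30% with seven grouped tests, and at most 71% to 80% if every listed measure is tested as though independent. All of these assume separate tests at 0.05, which is inferred, and no true effect. The lower end of the first two ranges uses an assumed correlation of 0.8. For the full list, correlations of 0.5 and 0.8 give 46% to 51% and 24% to 26%.

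Three stronger readings are tempting and are not supported:
- That the plan's error rate is 71% to 80%. This needs both a test for every laboratory item and independence, and the documents state neither.
- That there is no multiplicity adjustment at all. There is one, but it works within an outcome.
- That CD34+ cell number is the implied primary endpoint. The sizing uses it, but the synopsis objective omits it, Section 7 itself says the source studies differ greatly from this trial, and other sections point to migration.

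**What to change.** Before any unblinding, clinical or cellular:

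1. Name one primary endpoint, with its definition and unit, from an assay the protocol already describes. The choice is the sponsor's. For cell number, state whether it is CD34+ or CD34+/KDR+. Section 2 describes percentages in the mononuclear population, and no section describes an absolute count per mL for this trial. For migration, name the condition and say that the documents give no sample-size basis for it.
2. Name one decisive between-arm test at two-sided 0.05 with one time coding, for example the difference in change from week 0 to week 16.
3. Label the other cellular measures secondary or exploratory, and rest no claim of success on them.
4. Make the objective wording agree between the synopsis and Sections 2 and 6. Give the renal and exosome measures one status across the synopsis, Sections 2, 3 and 6, and Appendix A.
5. Say which within-outcome contrasts the Section 7 adjustment covers.

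If the sponsor wants no confirmatory endpoint because this is a pilot, the alternative is to state that all cellular results are exploratory and drop the p<0.05 success rule.

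The cost is protocol and SAP wording, with no new patients, and no new measurements if the endpoint comes from a described assay. The downside is that most gene, migration and colony results become supportive only.

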## INTRODUCTION

Diabetes affects more than 11% of adults in the United States and this is projected to nearly double by 2025. Both diabetes and obesity are associated with endothelial dysfunction, oxidative stress, endothelial cell inflammation, cardiovascular pro-thrombotic states and are the most common causes of kidney disease. Use of a sodium-glucose linked transporter (SGLT-2) inhibitor has shown promise in improving glycemic control, weight reduction, hypertension and even changes in circulating Renin-angiotensin-aldosterone system (RAAS) and nitric oxide (NO). However, whether these group of drugs have any effect on cardiovascular disease (CVD) risk modification or on endothelium or endothelial progenitor cells as a surrogate of cardiovascular and renal risk outcome measure, is unclear.

We have previously shown that CD34+ cells, derived from peripheral blood can act as a cellular biomarker that is more reliable than serum based markers for CVD risk estimation. Serum based inflammatory markers are not useful until the endothelium is already damaged and inflamed. Such serum based biomarkers takes several months to change and gives no preventive and predictable information as to whether a particular medication may affect future endothelium. This is why the study of endothelium progenitors is crucial. In our previous study of a prediabetes population with an aerobic exercise intervention, we have demonstrated that CD34+ cells are responsive to a change in therapy or intervention within 2-4 weeks and can be used as a reliable non serum based cellular bio-marker. CD34+ cells or endothelial progenitor cells have been used clinically to improve collateral circulation and have been extensively studied as a robust cardiovascular biomarker. Therefore studying CD34+ cells in patients, with or without Canagliflozin (Cana) can give vital information about the medication and its effect on endothelium. This is particularly important as another SGLT2 inhibitor Empagliflozin has shown unparalleled positive cardiovascular effects with an oral hypoglycemic agent. Of course, the question arises whether this clinical trial effect is secondary to glucose effect or direct effect of SGLT2 inhibitor on endothelium.

Multiple glucose transporters have been identified in human cells these include GLUTs, SGLTs and even taste receptors (such as TLR2 and TLR3). We know SGLT transporters are present in tubular cells and clearly blocking of SGLT2 in these cells is beneficial. Information on glucose transporter in stem or progenitor cells is almost nil. In our lab we have shown presence of GLUT1, SGLTs and TLR3 on CD34+ cells. We have also demonstrated that hyperglycemia is toxic to CD34+ cells, more than CD31+ positive mature endothelial cells. We hypothesize that blocking SGLT2 in CD34+ cells will be beneficial rather than detrimental. As far as glucose uptake in CD34+ cells are concerned other glucose transporters should be sufficient, in fact

lesser amount of glucose entry in a hyperglycemic milieu (type 2 DM patients) may be less pro-inflammatory and less pro-apoptotic.

Our preliminary data indicates that mRNA gene expression of both SGLT1 and SGLT2 are noted on human CD34+ cells however only SGLT2 mRNA gene expression is up-regulated several fold in human CD34+ cells in presence of hyperglycemia (20mM glucose). However non primary commercially obtained human endothelium (HUVEC) do not show similar results. An explanation could be SGLT2 expression decreases as the cell transitions from progenitor to mature endothelium. From these results we believe SGLT2 inhibitor will be effective on progenitors and not mature endothelium. We therefore hypothesize that CD34+ cells will be an ideal biomarker to study the effect of the drug. It is possible that Cana, by blocking SGLT2 receptors, may influence other CD34+ cell surface receptors including other glucose transporters and influence its function (most importantly migration). If a particular medication positively influences stem/progenitor cell migration then that medication can positively influence endothelial dysfunction and vascular complications from diabetes. We are particularly interested to note effect of Canagliflozin, a SGLT2 inhibitor on other glucose transporters such as GLUT 1 and 4 while looking at SGLT 1 and 2 on CD34+ cells. It will be helpful to discern these effects particularly when choice of oral diabetic medication in a type 2 diabetes population is practically limited to metformin, DPP4 inhibitors and SGLT2 inhibitors. We plan to investigate the effect of Cana on CD34+ cells, in a placebo matched study. We plan to recruit subjects with type 2 diabetes with the following characteristics: 1) overweight, mild and moderately obese (BMI=25.0-39.9); 2) individuals with type 2 diabetes with inadequate control, HbA1C= 7 to 10.0%, on any combination of the following anti-diabetic therapies: metformin (1-2 grams), insulin, GLP-1 agonists, a DPP-IV inhibitor, or sulfonylureas 3) with no current macrovascular complications. As per the ADA [2], Metformin, insulin, GLP-1 agonists, DPP-IV inhibitors, and sulfonylureas are all 1st line of care along with life-style modification. While Metformin on its own may affect inflammatory biomarkers, the effect is minimal at best, particularly in presence of endothelial dysfunction. For accurate comparison, both placebo and the Canagliflozin group will be on any combination of the following anti-diabetic therapies: metformin (1-2 grams), insulin, GLP-1 agonists, a DPP-IV inhibitor, or sulfonylureas We will recruit a total of 40 patients (20 individuals/per group) with approximately a 20% drop out rate over two years and we hope to retain 32 individuals (16/group). Individuals in each group will be matched by sex, age, and race. Participants will be assessed at baseline (week 0), and at 2 and 4 months of drug intake.

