**AVAILABLE RELATED STUDIES AND EXPECTED RESULTS:**

Studies measuring changes to EPCs in type 2 diabetes patients are very limited.

Use of CD34 positive cells as a cardiovascular risk surrogate has been reported in the past. Various studies, have shown that various disease states, including those seen in diabetes, can deplete and damage EPC, thereby diminishing their regenerative potential. The inability to maintain or repair damaged endothelial tissue leads to cumulative vascular dysfunction and cardiovascular disease.

*We hypothesize that monitoring number, function and gene expression of endothelial progenitors will allow us to quantify cardiovascular disease risk at the onset and regenerative potential post intervention at a cellular level. It will also help us to identify and correlate the best endothelial function bio-chemical inflammatory marker as an early indicator of cardiovascular disease progression in early type 2 diabetes and identify patients that are responders.*

Cana can influence the glucose transportation and modify intercellular glucose and cell energetics, and so it can influence the migration of the cell. SDF-1alpha, being a chemotactic agent, will also influence migration depending on its level.

Cana 100 mg or placebo will be added to patients who have type 2 diabetes with HbA1C of 7.0 to 10 % (both inclusive) while being on any combination of the following anti-diabetic therapies:

metformin (1-2 grams), insulin, GLP-1 agonists, a DPP-IV inhibitor, or sulfonylureas. As per ADA, Metformin is the 1st line of care along with life-style modification. While Metformin on its own may affect inflammatory biomarkers, the effect is minimal at best, particularly in presence of endothelial dysfunction. Also both the placebo and Canagliflozin group will be on any combination of the following anti-diabetic therapies: metformin (1-2 grams), insulin, GLP-1 agonists, a DPP-IV inhibitor, or sulfonylureas. Our study population will include equal numbers of adult male and female Type 2 diabetes (T2DM) patients aged 30-70 years, enrolled in both arms of the study.

Patients will be treated with 100 mg of Cana or placebo for 16 weeks. This time interval has been previously shown to be adequate to observe changes to Endothelial Progenitor Cells (EPCs).

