### **METHOD OF ASSIGNING SUBJECTS TO A TREATMENT**

Subjects, as per selection criteria below will be randomized to treatments using a permuted block design, developed by the Epidemiology & Biostatistics Research Core. This approach ensures groups will be approximately balanced at any time during the study and at study completion. Randomization will be performed by the MFA IDS Pharmacy staff who never come in contact with subjects.

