**Week -2:** Subjects will be phone screened to determine initial eligibility. If the phone-screening indicates possible eligibility, then the subjects will come to an in-person screening visit that same week (If within two weeks that is acceptable).

In-person screening (Week -2): Subjects will be screened and eligibility will be verified based on physical and laboratory tests. Equal numbers of male and female patients will be recruited.

**Week 0:** At this stage patients will be randomized into the study. Subjects will have the first set of measurements. We will make sure that patients still meet the inclusion criteria. They will be started on medication or placebo.

**Weeks 0, 8 and 16:** Subjects will all have the same measurements and will continue on study medication or placebo. All primary and secondary measures as outlined before will be carried out.

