### **DATA ANALYSIS**

Digital data files will be stored in a protected limited-access folder on the MFA network. Only the Study Biostatistician and the PI will have direct access to the data once it is on this server. The data file will have random subject identifiers and will have no HIPAA identifiers.

The distributional assumptions of all measures will be examined. Means and standard deviations will be computed for continuous measures and proportions for categorical variables. Graphical representations of the mean group slopes and individual slopes will be generated and inspected.

Study groups will be compared to determine whether any imbalance between the groups on patient characteristics remain after randomization. If imbalance is evident, by inspection, all models will be adjusted for the unbalanced covariates. Change in outcome over time will be examined using a multilevel approach with linear mixed models (LMM). The longitudinal multilevel modeling approach will enable us to examine characteristics of within-person change, as well as between-group differences that may influence change. LMMs handle missing data more efficiently than traditional ANOVA designs. In the linear mixed models, the patient is considered a random effect and the outcome measured at specific time points is nested within patient. Time (week 0, 8, 16) will be modeled as a continuous variable in order to assess linear effects from 0 to 8 to 16 weeks. In order to determine whether there are non-linear time effects (e.g., rapid increase from 0 to 8 weeks followed by little change from 8 to 16 weeks; or initial decrease at 8 weeks followed by increase at 16 weeks, etc.) we will also need to include models in which time is defined as a class variable (with 0 as the reference group). Subsequent analyses will add study group and other patient characteristics as covariates. We are particularly interested in whether there is a significant interaction between study group and time, adjusting for other patient level covariates. A significant interaction would indicate that the slopes in outcome over time differ by study group. If the global test of interaction is significant, subsequent significance testing of the pair wise comparisons of group slopes group will be adjusted for multiple comparisons. The model also includes coefficients for the group-by-time interactions and random effects for patient and time.

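### The plan promises arms matched by sex, age and race, but the only allocation method it describes is permuted blocks, with no stratification, minimisation or matching step

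*Combined protocol and SAP*

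**What the plan says.** Three statements in the combined protocol and SAP promise balance on patient characteristics.

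- Introduction: "Individuals in each group will be matched by sex, age, and race". No procedure, age band, race category or tolerance is given.
- Section 3, Available Related Studies and Expected Results: "equal numbers of adult male and female Type 2 diabetes (T2DM) patients aged 30-70 years, enrolled in both arms of the study".
- Study Design Overview, in-person screening at week -2: "Equal numbers of male and female patients will be recruited".

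Allocation is described once, in Section 4, Method of Assigning Subjects to a Treatment. Subjects "will be randomized to treatments using a permuted block design", and "This approach ensures groups will be approximately balanced at any time during the study and at study completion". No stratum, block size or covariate is named.

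Section 7, Data Analysis, then allows for imbalance: "Study groups will be compared to determine whether any imbalance between the groups on patient characteristics remain after randomization". The response is: "If imbalance is evident, by inspection, all models will be adjusted for the unbalanced covariates". The same section tests the group-by-time interaction with adjustment for other patient-level covariates, but does not list them.

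**The concern.** Permuted blocks control how many patients each arm has received at any point. They balance sex, age and race only on average over repeated allocations, and with 20 per arm a single allocation can fall well short of that average. Recruiting equal numbers of men and women fixes the overall sex ratio, not the ratio within each arm.

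Two things are at stake. First, a report that follows the Introduction would describe the arms as matched when nothing in the described procedure makes them so. Second, the analysis section closes the gap with covariates picked by looking at the data. It sets no threshold, gives no list, and does not say that the inspection comes before outcomes can be seen. The final model for many cellular, renal and vascular outcomes therefore stays open.

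**Working it through.** **Inputs.** 40 patients, 20 per arm, about 20% dropout, 16 per arm retained (Introduction). Equal numbers of men and women recruited, read as 20 and 20 (Study Design Overview). Permuted blocks with no stated strata (Section 4).

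**The plan's own figure.** 16 / (1 − 0.20) = 20 per arm, and 40 × 0.80 = 32 retained. Both reproduce. The matching statement itself carries no figure.

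**Sex split under blocks without strata.** Let X be the number of women in one arm. Then

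P(X = x) = C(20, x) × C(20, 20 − x) / C(40, 20), with C(40, 20) = 137,846,528,820.

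- P(X = 10) = 184,756² / 137,846,528,820 = 0.248.
- P(X = 9) = P(X = 11) = 167,960² / 137,846,528,820 = 0.205.
- P(X = 8) = P(X = 12) = 125,970² / 137,846,528,820 = 0.115.
- 12/8 or worse: 1 − 0.2476 − 2 × 0.2047 = 0.343.
- 13/7 or worse: 0.343 − 2 × 0.115 = 0.113.

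The formula treats the arm totals as fixed and ignores block size. Simulating blocks of 2, 4 and 8, with arrival order unrelated to sex, gives 24.7% for an exact split, 34.3% to 34.5% for 12/8 or worse, and 11.3% to 11.4% for 13/7 or worse. The unstated block size therefore does not matter.

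**Other factors (assumed distributions, because the documents give none).**

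- A trait held by 12 of 40 patients differs between arms by 4 or more in 30.1% of allocations. For a trait held by 8 of 40, the figure is 23.5%.
- The difference in mean age has standard error √(1/20 + 1/20) = 0.32 SD. It exceeds 0.5 SD in about 11% of allocations (normal approximation).
- Illustration only: for three independent 50/50 factors, the chance that at least one is 12/8 or worse is 1 − (1 − 0.343)³ = 0.72. The chance that all three split exactly is 0.248³ = 0.015.

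**Effect on the planned test.** Section 7 models weeks 0, 8 and 16 as responses and focuses on group by time. Take a 12/8 split.

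- If the sexes differ by a constant c at every visit, the arm means differ by (12/20 − 8/20) × c = 0.2c at week 0 and by the same 0.2c at week 16. The difference in change is 0.2c − 0.2c = 0. This is exact with complete data and approximate when visits are missing.
- If the sexes differ by d in change over time, the difference in change is 0.2d, or 0.3d for a 13/7 split. The documents give no value for d.

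**The case against.** The strongest reply has four parts.

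- **The list may be stratified.** Section 4 never says the blocks are unstratified. The scheme came from the biostatistics core, and a stratified list would fit the text. This stands. A reader might infer that the trial was in fact randomised without strata, but the documents show only that no stratification is described. If strata exist, Section 4 should name them.
- **Randomisation protects the comparison.** This stands. A reader might infer that the treatment effect is biased, or that a 12/8 split shifts the primary result by a calculable amount. The documents support neither. Chance imbalance is not systematic bias, and a constant sex difference cancels from the interaction. A shift needs a factor that modifies change over time, and nothing in the plan says how large that would be.
- **The analysis already expects imbalance and adjusts for it.** This stands in part. Section 7 does not rely on matched arms. But adjusting for whatever looks unbalanced is selection from the data, and a main-effect term for sex would do almost nothing for the interaction test.
- **The sentence is loose Introduction wording in a pilot.** Section 3 repeats the promise for sex and ties it to both arms, so it is not one stray phrase. If it is loose, correcting it costs nothing.

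**Conclusion.** The stated balance is a property that the described allocation does not deliver. For sex, exact equality would be met in about one allocation in four, and a 12/8 split or worse would occur in about one in three. These two figures assume exactly 20 men and 20 women and blocks without strata. The 72% for three factors also assumes independent 50/50 factors and takes 12/8 as the mark of imbalance, so it is an illustration.

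The consequence is limited. The arms cannot be reported as matched, imbalance matters to the main test only through factors that modify change over time, and the covariate set is left to judgement after the data are seen. None of this invalidates the randomised comparison. The point is worth correcting because the correction is cheap.

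**What to change.** 1. **Section 4.** Stratify the permuted blocks by sex and say so. The split within each sex is then near-equal, and exact only if each stratum fills complete blocks. With blocks of 4, two strata of exactly 20 give 10/10, and an incomplete block leaves a difference of at most 2 in that stratum.
2. **Introduction and Section 3.** Replace the matching statement with one saying that allocation is stratified by sex. Align the Section 3 sentence on men and women in both arms with it.
3. **Section 7.** Replace adjustment by inspection with a list fixed before unblinding: sex, age and race, with their interactions with time if they are meant to protect the group-by-time test. Do not add the baseline outcome as a further covariate. Week 0 is already a response in the model, and baseline is handled there.

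Stratifying on all three factors would be thin. With two levels each there are 8 cells averaging 40/8 = 5 patients. Under the same 50/50 assumptions, the illustrative 72% would fall to about 3% with blocks of 2 or 15% with blocks of 4, but arm totals would then differ by 4 or more in about 12% and 23% of allocations.

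**Cost.** A second randomisation list at the pharmacy, a few sentences, and a few degrees of freedom. With race in two groups (assumed), the three time interactions add 3 terms with linear time, or 6 with time as a class variable.

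**If allocation is already complete,** correct the matching statements and fix the covariate list before unblinding.
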